8. For multi-center studies, number of participants approved for accrual study-wide (University of Alabama site plus all other sites).	
9. For multi-center studies, number of participants enrolled study-wide (University of Alabama site plus other sites).	
10. Number of withdrawals from the research (since last approval date) and explanation/reasons for withdrawals.	
11. Description and number of:	

a) Reportable Protocol Deviations/Violations since the last approval date:

0

b) Serious Adverse Events (SAEs) or unanticipated problems involving risks to participant or others since the last approval date:

0

12. Have there been any complaints about the research during the last year? N
If yes, please describe.

13. **Briefly describe the progress of the study to date.**

Data collection has been completed. Analysis is underway.

14. Is there a Data Safety Monitoring (DSM) plan for this study?

No

Yes, a copy of the DSM report(s) for the last approval period is attached.

Yes, but a copy of the DSM report(s) for the last approval period is not attached. Please explain below.

15. FDA Regulated Studies

Is this a Food and Drug Administration (FDA) Regulated Study, (i.e., N
involves drugs, devices, biologics)? If yes, please answer the following
questions:

a) Have there been any changes in the FDA status
of any drug or device used in the study?

If yes, please explain:

b) Have any of the investigational drugs or devices
used in this study received FDA approval?

If yes, please explain:

c) Have any new alternative drugs or devices been
approved for treatment of the study condition that
may affect participants willingness to participate?

If yes, please explain:

Have current participants been notified? Please explain:

- d) Has there been a change in the standard care that may be considered as an alternative to the investigational drug or device or that would affect the original study design?

If yes, please explain:

Have current participants been notified? Please explain:

- e) Is there any new information that might affect the risk/benefit ratio and the willingness of current study participants to participate or to continue to participate in the research?

If yes, please explain:

Have current participants been notified? Please explain:

- f) Is there any new information about study as a whole, the drug, or device that needs to be provided to past participants

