Mixed Design (Between/Within Subjects) Pre-test/Post-test Comparison

d) **Provide a timeline for individual participant recruitment and follow-up (analysis for the study is required).**

Participants will be recruited from various sources including the UA Participant Registry, DS Connect (NIH Registry of individuals with Down syndrome interested in research), local schools, and local service providers. Following initial contact by these various sources, participant families will self-identify to receive additional information about the study - including a copy of the Parental Consent. The study will take place over the course of 4 months for each participant. All participants will receive the PPVT, the KBIT 2 Matrices subtest, an assessment of Mental Rotation, and an assessment of Visual Perspective Taking during the first testing session (Approximately 45 minutes). Mental Rotation and Perspective Taking performance will be assessed two additional times for all participants, once following Experience Session 16 and once following Experience Session 32. These two assessments will take approximately 15 minutes. Experience sessions will be provided twice per week, with each session lasting approximately 30 minutes over a period of 16 weeks. Half of each group (No Delay participants) will begin spatial ability experience during a first experience session scheduled approximately one week following the initial assessment. The other half of each group (Delay participants) will not begin the spatial ability experience for the 8 weeks following the first assessment and serve as a control for practice effects on the assessment measures. The Delay participants will receive a second assessment on the Spatial Abilities and begin spatial ability experience during week 9. They will receive the same protocol as the experimental participants following the second assessment (8 weeks experience, ability assessment, 8 weeks experience, ability assessment). The final assessment will come following Experience Session 32 (week 16). Data analysis is planned upon the completion of all data collection during year 03 of the

project period.

e) Will participant be randomized? Y

f) If participants will be given placebo, please justify placebo use, and describe contents of the placebo. Y

NA

3) Study Procedures

a) Is this project a multicenter study (i.e., same project is conducted elsewhere by a different investigator)? Y

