Mental Rotation Assessment - On each trial, participants will be presented a geometric shape (e.g., a block letter L) in the center of a computer screen that completes one of two rectangles presented at the bottom of the same screen. The open area in one rectangle is the mirror image of the open area in the second rectangle. The shape in the center of the screen will fit one of the rectangles when horizontal. The shape can be rotated from horizontal by 0, 45, 90, 135, 180, 225, 270, or 315 degrees. Participants respond by touching the rectangle into which the shape will fit once oriented properly (using touchscreen technology). Participants receive 4 trials at each orientation.

Perspective Taking - Participants will be seated at a table with four chairs and four different objects (street lamp, mailbox, stop sign, traffic signal) representing each location on the corner of a city block in front of each chair. A stuffed animal is placed behind each object. One experimenter walks around the table stopping at each location. At each location, the participant is told that the experimenter is taking a picture from that location and he/she is asked to look at four pictures. The task is to select the picture that the experimenter has just taken. The four pictures consist of the participant's point of view, a mirror image of the participant's point of view, the experimenter's point of view, and a mirror image of the experimenter's

Due to CoVid Restrictions, Procedures were adapted for online presentation via Zoom. Ravens and PPVT-4 used available commercial formats. Mental Rotation and Perspective Taking involved the creation of Video presentations. Online presentation was approved by the University IRB on 03/04/2020.

point of view. This task will take 5 - 10 minutes.

Assessments 2 and 3 will include only Mental Rotation and Perspective Taking Assessments.

Spatial Ability Experience will include two tasks of Object manipulation and two Large Environment Experiences. These tasks are meant to provide experience.

Object Manipulation Experience: Two categories of tasks will be used to provide object manipulation experience: LEGO Block Play and Puzzle Construction. One task will be used in each spatial ability experience, with tasks alternating between sessions.

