c) Provide stopping rules for the study. If the proposed study is a clinical trial where a drug, vaccine, device or other treatment is compared to a placebo group or comparison treatment group, what are the guidelines or endpoints by which early decisions regarding efficacy or lack of efficacy can be made? For example, it may be reasonable to stop enrollment on a study when efficacy has already been clearly demonstrated, to avoid unnecessary enrollments of additional participants. Alternatively, it may be reasonable to stop enrollment when it is clear that efficacy will never be demonstrated, given the statistical power of the study as designed. Describe the guidelines that are in place to assist in making these determinations, if relevant to the proposed study.

NA

d) Describe how data analysis will be performed (statistical tests, methods of evaluating data) and indicate the smallest group/unit for which separate reporting will occur. For studies involving a questionnaire, if data and reliability information are available, please describe or provide references. (Page numbers from a sponsor's protocol/grant may be referenced in this section).

The independent variables of interest will be Group (DS and TD), Delay (No Delay and Delay), and Assessment (1, 2, and 3). The smallest number of participants in any given cell of the design is 20 participants.

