Specific Aim 1 evaluates the malleability of MR and PT performance in participants with DS. Consistent with Aim 1, we will apply Multivariate ANOVA to the subsample of DS children. If the test for sphericity is significant, we will interpret the multivariate tests for the within subject effects. If not, we will use the univariate tests due to their increased statistical power. With either option, the test for the effect of Assessment, if significant, would indicate that performance of the DS children improves over time. We will then evaluate the interaction of AssessmentDelay, which if significant would signify that Delay vs No Delay participants exhibit a different magnitude of improvement across Assessment times. One contrast of interest compares Delay vs No Delay participants at Assessment 2. Performance favoring the No Delay participants would indicate a significant effect of spatial ability experience. A second contrast of interest compares Assessment 3 performance to Assessments 1 and 2 for the Delay participants. If we are able to confirm that the Delay participants exhibit higher scores at Assessment 3 than at Assessments 1 and 2 (which should not differ) then the benefits of spatial ability experience for persons with DS would be further confirmed.

Specific Aim 2 evaluates possible differences in rate and magnitude of improvement of DS and TD participants. We will approach Aim 2 in a very similar statistical manner. For Aim 2a, we will apply Multivariate ANOVA to the whole sample to test for the effect of AssessmentGroup. If significant, it is indicative that DS and TD participants do not exhibit the same degree of improvement following training. If improvement in performance is greater for the participants with DS, it

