General Information: Potential recruitment sites are identified and we provide them with information about the study. We ask them to identify potential participants and to send recruitment and consent information to the parents/guardians of the identified individuals. We do not get any identifying information on individuals at this point in time. Participants self-identify to the researchers by returning signed consent forms with contact information or by requesting additional information about the study. We will not contact any individuals who have not identified themselves as interested in the study. Information to be discussed with recruitment sites and a draft letter for them to send to parents/guardians is attached.

The University of Alabama participants with DS will be recruited from the University of Alabama Intellectual Disabilities Participant Registry that was established with NICHD Recovery Act Funding ([name], PI). Participants will also be recruited through local DS organizations like DS Alabama, DS Connect, and through local public schools. Montclair State University participants with DS will be recruited from local service providers, DS Connect, and local public schools. The lead PI at Montclair State has established research relationships with these organization in the past several years. Twenty-four participants will be tested at UA and 24 at Montclair State University.

Typically developing children will be recruited from local preschools and elementary schools, including The University of Alabama Children's Program and the Montclair State University preschool program. Twenty-seven participants will be recruited from each site.

We have secured permission from the CDRC (see attached permission email) and recruited typically developing children from that site. We are adding the following organizations for recruitment and will be contacting them about recruitment following approval of the new recruitment materials. We will be identifying additional recruitment sites in the future that will be added to the list once contact is made.

<https://childrenhelpingscience.com/>
Massachusetts Down Syndrome Congress
Global Down Syndrome Organization
New Jersey Down Syndrome Organization

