2. Address procedures you will use to ensure the participant's representative has been told of his/her obligation to try to determine what the prospective participant would do if competent, or if the prospective participant's wishes cannot be determined, what the participant's representative thinks is in the incompetent person's best interests:

N/A

3. The VA has specific requirements and procedures for determining and documenting in the person's medical record that an individual is incompetent or decisionally-impaired. There are additional requirements if the lack of decision-making capacity is based on diagnoses of mental illness. These requirements are outlined in the Veterans Health Administration (VHA) Handbook 1200.5, Section II. Have you reviewed these requirements and included them in your procedures?

4. Justify that the research involves no significant risks, or if the research presents probability of harm, justify that there is at least a greater probability of direct benefit to the participant:

N/A

Note:[Veterans Health Administration Handbook 1200.5, July 15, 2003, Section 11 - Research Involving Human participants with Surrogate Consent, and Appendix D Vulnerable Populations, Section 6(c)]

Section 4.

For research involving cognitively impaired persons outside the state of Alabama, also complete this section.

a) Provide information regarding the state definition of legally authorized representative, child, decisionally-impaired, or guardian, as applicable to the research and to the federal definitions. [If the research is to be conducted in more than one state outside of Alabama, provide this information for each state.]

Note that because recruiting will extend beyond the two states, will will follow the procedures outlined below to identify and obtain consent for participants and legally authorized representatives.

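### Site is in no model, and with Down syndrome accrual closed at 30 of 48 its planned balance across groups is no longer assured; Aim 2 should adjust for it

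*Combined protocol and SAP*

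**What the plan says.** - **Model.** Section 3(d) names the factors: "The independent variables of interest will be Group (DS and TD), Delay (No Delay and Delay), and Assessment (1, 2, and 3". For Aim 2 it says "we will apply Multivariate ANOVA to the whole sample to test for the effect of AssessmentGroup". Neither aim has a Site term, a site contrast or a site sensitivity analysis.
- **Planned site split.** Section 7(f) says of the DS group: "Twenty-four participants will be tested at UA and 24 at Montclair State University". Of the TD children it says: "Twenty-seven participants will be recruited from each site".
- **Achieved numbers.** The continuing review form (items 4, 5 and 7) reports 54 TD children and 30 DS participants, 84 in all, against 54 and 48 approved. Item 13 adds: "Data collection has been completed. Analysis is underway". No breakdown by site is given.
- **Randomisation.** Section 2(e) reads "e) Will participant be randomized? Y", and section 2(d) puts half of each group in each Delay arm. Stratification by site is not mentioned.
- **Changes in conduct.** Section 3(b) records: "Due to CoVid Restrictions, Procedures were adapted for online presentation via Zoom". The section on cognitively impaired participants (Section 4, item a) states: "Note that because recruiting will extend beyond the two states".

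**The concern.** Group is not randomised, so the DS-TD difference in gain is protected only by matching and by balance on anything else that affects gain. The planned split gave that balance for Site: each site would hold half of the DS group and half of the TD group, and a site difference in gain common to both groups would cancel.

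A shortfall of 18 DS participants with the TD group full removes that assurance. Section 3(d) does not appear to have been revisited since: it still gives 20 as the smallest cell, whereas 30 DS participants over two Delay arms average 15.

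The Aim 2 contrast carries a substantive reading. Greater DS gain is to be taken as evidence that experience may be a main source of the initial difference between groups. If one site produced larger gains and also tested a larger share of the DS group, part of that site difference would be read as a group difference. With the imbalance reversed, it could mask one.

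**Working it through.** **The plan's own figure.** The section on children (Section 2, item c) gives a detectable f(V) of 0.27 for 4 groups x 3 assessments, N = 96, alpha 0.05 and power 0.80. With df 6 and 184 and noncentrality 0.27² x 96 x 2 = 14.0, power is 0.797; the detectable f(V) at 80% power is 0.271. The figure reproduces, and it contains no Site term.

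**Inputs from the documents.** Planned 24/24 DS and 27/27 TD; achieved totals 30 DS and 54 TD.

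**Inputs assumed.**
- The TD group reached its planned 27/27.
- No site tested more than its planned 24 DS participants, so the split lies between 15/15 and 24/6.
- The correlation between assessments is 0.6.
- The site difference in gain is 0.5 or 0.3 SD of a single assessment score.
- Gain between two assessments stands in for the three-assessment test.

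**Bias.** Bias = (DS share at a site - TD share at that site) x site difference in gain.
- Planned: 24/48 - 27/54 = 0, so no bias.
- 24/6: (0.80 - 0.50) x 0.5 = 0.15 SD.
- 20/10: (0.667 - 0.50) x 0.5 = 0.083 SD.
- 18/12: (0.60 - 0.50) x 0.5 = 0.05 SD.
- 15/15: nil.

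**Standard error.** Within-site variance of gain = 2(1 - 0.6) = 0.8. The SE of the DS-TD difference = sqrt(0.8) x sqrt(1/30 + 1/54) = 0.204 SD. The 24/6 bias is 0.15/0.204 = 0.74 SE.

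**Residual variance.** Leaving Site out shifts the estimate, but it also puts the site difference into the residual, and this makes the test more conservative. At 15/15 with 0.5 SD the residual variance becomes 0.8 + 0.25 x 0.5² = 0.8625. The effective critical value rises from 1.96 to 1.96 x sqrt(0.8625/0.8) = 2.035, and the error rate falls to about 4.2%. Holding the SE at 0.204 instead would give 11.4% at 24/6, which is too high.

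**Two-sided error rate with no true DS-TD difference, Site omitted.** Simulated with a pooled t-test; ranges show the spread between separate runs.

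| DS split | 0.5 SD | 0.3 SD |
|---|---|---|
| 15/15 | about 4% | 4.7% |
| 18/12 | 4.6 to 4.8% | 4.9% |
| 20/10 | 5.7 to 6.0% | 5.3 to 5.4% |
| 24/6 | 10% | about 7% |

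If the site difference is expressed in SDs of gain instead, no correlation is needed. The 24/6 rate is then 9.1% at 0.5 SD and 14.6% at 0.8 SD.

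**With Site in the model.** The error rate returns to about 5% in every scenario. The variance of the Group contrast is multiplied by 1.00 (15/15), 1.01 (18/12), 1.04 (21/9) or 1.09 (24/6).

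**The case against.** The strongest reply is that nothing shows a site difference in gain.
- Assessments moved to Zoom with common commercial or video formats.
- Both sites list DS Connect and local public schools as DS sources. Organisations tied to neither site were added, and recruitment went beyond the two states.
- Research assistants were to be trained and observed by the faculty, two at every testing session, with bi-weekly meetings across sites (section on children, Section 2, item h; section 8b).
- Differences in who was recruited mainly shift baseline level, which drops out of Assessment x Group.

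All of this stands as reason to expect a smaller site difference. It does not remove the issue. No section says that one team did all the testing, each site kept its own investigator, and the block play depends on the experimenter's part in it.

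It is also fair that the error rate stays at or below nominal up to about 18/12. Material inflation needs both a lopsided split and a sizeable site difference.

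Two stronger readings do not follow. A reader might infer that the DS-TD comparison is already confounded by site; the documents report no split, and at 15/15 against 27/27 there would be no bias. A reader might also infer that missing stratification biases Aim 1. Delay is randomised, so a chance imbalance by site affects precision, not validity, and the documents give no basis for sizing that loss.

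**Conclusion.** The point holds as a gap in the Aim 2 model. The planned equal split was what kept Site out of the Assessment x Group contrast; it is no longer assured, and the analysis has nothing in its place. Under the stated assumptions the bias is between nil and 30% of the site difference in gain: 0 to 0.15 SD for a 0.5 SD difference, with an error rate from about 4% to 10%, and about 5% to 7% at 0.3 SD.

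These limits depend on two planned figures having held: 24 per site, which section 7(f) states as a plan and not as a cap, and TD at 27/27, of which only the total of 54 is confirmed. If all 30 DS participants came from one site, the share difference would be 0.5. The correlation and the site differences are assumptions, and Zoom delivery and shared recruitment may make the true site difference smaller. For Aim 1 the matter is precision only.

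**What to change.** 1. Define Site as the testing team (University of Alabama or Montclair), since Zoom and out-of-state recruitment make location ambiguous.
2. Confirm now that it can be recovered for every participant. No section lists Site as a data field. Section 10(c) has each site's investigator keep a master list but also says identifiers are removed once a participant's data collection is complete.
3. Report Group x Delay x Site counts. These show at once how large the imbalance is.
4. Add Site and Site x Assessment to the Aim 2 model, and to the Aim 1 model at least as a sensitivity analysis. As analysis is under way, record the date of the change and whether results had been seen.

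The cost is a few degrees of freedom (1 for Site and 2 for Site x Assessment), plus up to about 9% more variance in the Group contrast at a 24/6 split and almost none near balance. In Aim 1, with 30 DS participants, the extra terms could lose a little precision if the sites do not differ, which is why a sensitivity analysis is enough there.

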*** Continuing Review ***

Continuing Review/Annual Report

WHAT TO UPLOAD WITH YOUR CONTINUING REVIEW APPLICATION

For studies where research activities are limited to data analysis, upload participant safety information and publications (e.g., manuscripts, abstracts) since the last IRB approval, if applicable.

For all other studies, upload:

- â€¢ A clean (unstamped) copy of consent/assent document(s) to be stamped upon IRB approval.
- â€¢ Participant safety information including the most current Summary of all serious adverse events and unanticipated problems involving NSKS to participants or other and data safety monitoring reports since the last IRB approval, if applicable.
- Any publications (e.g., manuscripts, abstracts) since the last IRB approval.

Any changes, updated and/or new study materials should be uploaded and questions 19 - 24 of this form should be completed.

1. Please indicate the status of the study:

- a) The study has not started but will become active.
Please explain why the study has not started.
- b) The study is ACTIVE (please check the appropriate box below):
Study is open to accrual.
Study is on hold or halted.

Please explain what needs to occur before accrual can resume:

Study is permanently closed to accrual.

- i. Y Have all participants completed all research related activities/interventions?
- ii. N/A Will the research only remain active for long-term follow-up of participants?
- iii. Y Are remaining research activities limited to data analysis only?

For IRB office use: * may qualify for expedited review

c) The study has expired and needs to be re-initiated.

Explain any research activities occurring during lapse in IRB approval.

2. Date the study was initially approved by the IRB:	
3. Approval date of previous continuing review:	
4. Total number of participants/records/specimens approved to date.	
5. Total number of participants that have given consent (verbal or written) to date.	
6. Total number of participants that failed screening(if not applicable, state N/A).	
7. Total number of participants accrued since the beginning of the project.	

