*** * * Subject Population(a-h) * * ***

7. Subject Population - In the space below, please detail the participants that you are requesting to recruit (include description of each group requested)

a) Expected age range of participants. (For example - 19 yrs to 90 yrs).

Participants with Down syndrome will be between 10 and 30 years of age.

Typically developing children will be between 4 and 9 years of age.

We will test 48 participants per group - plus an additional 6 typically developing children as needed to provide a closer match on nonverbal ability for the children in the Experimental condition with the children in the control condition.

b) i) Number to be directly solicited for this research.
 
ii) Number to be consented (including withdrawals or screen failures)
 
iii) Number expected to complete the study.
 
c) If this is multi-center study, number of participants to complete the study study-wide
 
d) If study involves review of medical or other records, number of records to be reviewed.
 
e) If women, minorities, or minors are excluded, a clear compelling rationale must be provided unless not applicable. Examples for not including minors: disease does not occur in children; drug or device would interfere with normal growth and development; etc.
 
f) Describe how potential participants will be identified for recruitment (e.g., chart review, referral from individual's treating physician, those individuals answering an ad). How will potential participants learn about the research, and how will they be recruited (e.g., flyer, e-mail, web posting, telephone, etc.)? State where recruitment materials will be located. Click "Add" to upload recruitment materials document.
	
X N/A
 
N/A
 
102
 
102
 
N/A
 
102
 
X N/A
 
NA

--	--

Important to remember: Study Activities cannot begin until IRB approval is granted.

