The children used in this study are necessary for providing a comparison group matched on non-verbal ability with participants with Down syndrome. In this type of research, it is necessary to evaluate the performance of individuals with Down syndrome against participants who are matched on general ability measures to determine if the difficulties associated with Down syndrome are beyond that which would be expected based on developmental level.

b) Has this research been conducted in adults? Y

If yes, is there any indication that the proposed research would benefit, or at least not be harmful to children?

Similar research has been conducted in adults and children with no adverse effects. The children are essential for providing a comparison group for the participants with Down syndrome.

c) Indicate how many children you propose to enroll in the study and justify this number (whenever possible, involve the fewest number of children necessary to obtain statistically significant data which will contribute to a meaningful analysis relative to the purpose of the study).

All of the typically developing participants will be children (48 participants originally planned). Many of the participants with Down syndrome will also be participants (we anticipate about half of the 48 participants in this group, or 24). The total number of participants was determined by power analysis. A 4 groups x 3 repetitions analysis with alpha set at .05, power set at .80, and total N = 96 (24 in each group) would be sufficient to observe a significant effect size (f(V)) of .27 or greater. To evaluate the power for simple effects tests to compare the effects of training for the DS and TD participants separately, we conducted a 2 groups (Delay and No Delay) x 3 repetitions analysis with alpha set at .05, power set at .80, and total N = 48 (24 in each group). Power analysis indicated that 48 total participants would be sufficient to observe a significant effect for effect sizes (f(V)) of .27 or greater for main effects of Delay and of .25 or greater for main effects of Assessment Time. Power calculations were conducted in GPower 3.1.9.2 (Faul et al., 2007). However, we are requesting an additional 6 typically developing participants at this time to make it possible to better match the Experimental and Control group children on nonverbal ability.

d) Describe how assent of a child will be obtained and documented (if applicable). If not applicable, explain why.

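### The stated minimum cell of 20 cannot hold: 30 Down syndrome participants in two arms leave at most 15 in the smaller one, and the detectable effects for that group assume 48

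*Combined protocol and SAP*

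**What the plan says.** Section 3(d) names the factors as Group (DS, typically developing [TD]), Delay (No Delay, Delay) and Assessment (1, 2, 3), and adds: "The smallest number of participants in any given cell of the design is 20 participants".

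The planned numbers are in two places. Section 7(a) says "We will test 48 participants per group", with up to 6 further TD children. The sample size justification (Research Involving Children, Section 2, item c) assumes 24 in each of four cells, total N = 96, with f(V) = .27. For each group analysed separately it gives: "48 total participants would be sufficient to observe a significant effect for effect sizes (f(V)) of .27 or greater for main effects of Delay". The corresponding figure for Assessment Time is .25, at alpha .05 and power .80.

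The achieved numbers are in the Continuing Review form. Item 5 gives 54 children and 30 DS consented, against 54 and 48 approved in item 4. Item 9, the "number of participants enrolled study-wide (University of Alabama site plus other sites"), is 84. Item 1(b) is answered "Y Have all participants completed all research related activities/interventions", and item 13 reads "Data collection has been completed. Analysis is underway".

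On allocation, section 2(d) says "Half of each group (No Delay participants) will begin spatial ability experience" first, and the other half wait. Aim 1 is tested in the DS subsample alone, where "One contrast of interest compares Delay vs No Delay participants at Assessment 2".

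**The concern.** The minimum cell size is written in the present tense in a submission that also reports closed accrual, and the two disagree. The disagreement falls on the DS group, which alone carries Aim 1. Someone who takes cell size from 3(d) and detectable effects from the sample size justification would credit the DS tests with at least 20 per cell and with the sensitivity of a sample of 48. Neither applies to 30. The practical risk is in interpretation: a non-significant Delay contrast in DS could be read as evidence that experience does not help, when the sample could reliably detect only large differences.

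**Working it through.** **1. Cell size.** 30 + 54 = 84, which matches the study-wide enrolment, so 30 is not one site's count. For any split a and 30 − a, the smaller arm is at most 30/2 = 15. Two cells of 20 need 2 × 20 = 40. The plan itself gives 48/2 = 24. So 20 equals neither the planned nor the achievable cell, and no section derives it.

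**2. Reproducing the plan's power figures** (noncentral F, alpha .05, power .80, m = 3 assessments, k groups).
- Four groups, N = 96: λ = f(V)² × N × s with s = 2, df 6 and 184. The detectable f(V) is 0.271, and power at .27 is 79.7%. The stated .27 reproduces.
- Two groups, N = 48, read as f(V): s = 1, df 2 and 45, required λ = 10.306. Assessment (or Assessment-by-Delay) gives √(10.306/48) = 0.46, not .25. Delay with λ = f² × N gives √(8.190/48) = 0.41, not .27.
- Two groups, N = 48, read as Cohen's f with a common correlation ρ: Delay f = √[λ(1 + 2ρ)/(3N)]; Assessment f = √[λ(1 − ρ)/(3N)]. At ρ = 0.14 these are √(8.190 × 1.28/144) = 0.270 and √(10.306 × 0.86/144) = 0.248. Solving for ρ gives 0.141 from .27 and 0.127 from .25 (multivariate). At ρ = 0.5 they would be 0.34 and 0.19. The plan states no ρ.

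**3. From N = 48 to N = 30.** The detectable effect is proportional to √(λ/N), and the factor in ρ cancels in the ratio.

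| Test | df at 48; at 30 | λ at 48; at 30 | Ratio of detectable effects | Power at N = 30 for an effect with 80% at N = 48 |
|---|---|---|---|---|
| Delay | 1, 46; 1, 28 | 8.190; 8.424 | √[(8.424/30)/(8.190/48)] = 1.283 | 59% |
| Assessment or Assessment-by-Delay, multivariate | 2, 45; 2, 27 | 10.306; 10.789 | 1.294 | 57% |
| Assessment, univariate | 2, 92; 2, 56 | 9.955; 10.169 | 1.278 | 58% |

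For scale only, if the N = 48 figures are Cohen's f with ρ = 0.14, Delay goes from 0.27 to 0.35 and Assessment (multivariate) from 0.25 to 0.32. In f(V), Assessment goes from 0.46 to 0.60 and Delay from 0.41 to 0.53. The two scales must not be compared with each other.

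**4. Delay versus No Delay at Assessment 2,** as an unadjusted two-sample comparison with n per arm. Detectable d = √(2λ/n); 95% CI half-width = t × √(2/n).
- n = 24: √(2 × 8.190/24) = 0.83 SD; half-width 2.013 × √(2/24) = 0.58 SD.
- n = 15: √(2 × 8.424/15) = 1.06 SD; half-width 2.048 × √(2/15) = 0.75 SD. Power at 0.83 SD is 59%.

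**5. Four-group analysis at N = 84.** With s = 2, df 6 and 160, the detectable f(V) is 0.29, assuming equal cells. With 30 DS and 54 TD the cells are not equal, so this is approximate.

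**The case against.** The best defence is that the sample size justification is a design calculation, explicitly conditional on N = 48, and that the shortfall is disclosed in the Continuing Review form of the same submission. That stands. A reader might infer that accrual has made the power analysis wrong; the documents do not support this, since it never claimed to describe 30 people.

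A reader might also take 20 to be a planning number that nobody updated. The plan's cell is 24 and the source of 20 is undocumented. It could be an attrition allowance or a reporting minimum, since the form item asks about the smallest unit reported separately. Neither reading rescues the sentence: as a count of the design's cells it is contradicted by accrual, and as a reporting floor it would exclude at least one DS arm.

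It is tempting to call the f(V) label on the N = 48 figures a proven mistake. The correlation of 0.13 to 0.14 is back-fitted, so this is an inference. The N = 96 figure is sound as labelled.

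The 0.83 and 1.06 SD values assume no baseline adjustment, and 3(d) does not specify the contrast that closely. With adjustment at an assumed baseline correlation of 0.5, both shrink by √(1 − 0.25), to about 0.72 and 0.92 SD. The relative loss is the same.

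Finally, 54 TD children consented against 48 originally planned does not prove that the TD analyses keep their planned precision. Consented is an upper bound for analysed in both groups, and the zero withdrawals in item 10 cover only the time since the last approval.

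**Conclusion.** The minimum cell size in 3(d) is wrong for the DS group: at most 15, not 20. This rests only on the reported counts and the two-arm split. Fifteen per arm is the best case, because the actual split and the number analysed are not reported.

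The N = 48 detectable effects are not errors of planning, but they do not describe the DS sample analysed for Aim 1. At N = 30 detectable effects are 28% to 29% larger, and power falls from 80% to about 57% to 59% for an effect of the planned size. These relative figures hold for any common within-person correlation; the absolute values do not. The metric of the N = 48 figures is a secondary matter needing clarification.

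Nothing here invalidates a test or the trial. It should be fixed because it misstates the size of the group behind the main aim.

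**What to change.** 1. In 3(d), correct the minimum cell size and add achieved and analysed counts for each of the four cells beside the planned ones (DS 24 per arm; TD 48 in total originally, up to 54 as amended).
2. Keep the power figures in the sample size justification, labelled as applying to planned N = 48 and N = 96. State the metric and the correlation behind the N = 48 figures.
3. Beside them, give the DS-only detectable effect or expected CI half-width at the achieved N, in one declared metric (28% to 29% larger than planned if all 30 are analysed). For the four-group analysis, give f(V) of about 0.29 at N = 84, noting the equal-cell assumption.
4. Report 95% CIs for the DS contrasts, and state that a non-significant DS result will not be read as no effect.

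The cost is wording only: no test, dataset or enrolment changes. The changes requested in the Continuing Review form concern personnel only, so a new amendment may be needed. The downside is that the stated DS figures become less favourable.
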